## **7.2. Descriptive measure (CP assessment)**

The participant's CP will be described during visit 2, using the Australian Spasticity Assessment Scale (ASAS), Manual Assessment Classification System (MACS) and the Gross Motor Function Classification System (GMFCS) and the Communication Function Classification System (CFCS). In addition, the presence of active epilepsy, controlled epilepsy or no epilepsy will be recorded. Other eligibility criteria will be addressed during the physical examination.

### 7.3. Evaluative measures

Evaluative measures will be taken at baseline prior to infusion (visit 2) and after intervention at follow-ups visits defined below. A copy of the assessment results at baseline and final assessment will be available for families if they would like them.

#### Motor assessment (baseline and at visits 7 and 9)

The gold standard gross motor measure for CP, the Gross Motor Function Measure (GMFM-66) will be used. The GMFM-66 has good validity and reliability, and is the only gross motor measure responsive to change for children [59]. The assessment can be scored from videotape if needed. 45 mins to complete (participant)

An upper limb assessment will also be used, the Quality of Upper Extremity Skills Test (QUEST). This tool is validated for use with children aged 18 months to 8 years and has been used in the older range needed for this study [60]. Results will be reported for each limb separately. This tool is reliable and sensitive to change, but has the disadvantage that it measures impairment reduction rather than functional improvement. The QUEST can be scored from videotape if needed. 15 mins to administer (participant)

#### Quality of life assessment (baseline and at visits 7 and 9)

Assessors will use the Cerebral Palsy Quality of Life Questionnaire (CP-QOL) for validated for adolescents 13-18 years old, or for children less than 12 years the CP QOL-Child. This measures social wellbeing and acceptance, feelings about functioning, participation and physical health, emotional wellbeing and self-esteem, access to services, pain and impact of disability and family health. Some of these items are not expected to change over the course of this study. It is completed by the participant's caregiver, and also by the participant for 9-18 year old [61, 62]. 15-25 mins to complete (parent and participant)

#### Cognitive assessment (baseline and at visit 9)

No specific cognitive training programs have been validated for use with children with CP, however the limited evidence available indicates there may be some spontaneous improvement in cognition. Therefore, cognition will be assessed by a psychologist in an age appropriate manner (see Table 2 below), ensuring that an individual is tested using the same tool before and after the intervention. There is a possible learning effect with cognitive assessment tools, in that using them too often leads to familiarity with the tool which confounds data on actual change in cognition, therefore most tools are recommended for use only every 12 months. Therefore, we will avoid assessing cognition at the 3 and 6 month assessment visits but will assess at baseline (-1 month) and 12 months. Note that this assessment may not be possible for children with extremely severe CP. 1 hour to administer (participant)

Table 2: Cognitive assessment tools for each age range.

Age Range (at baseline)	Assessment tool
1-2.5 years (validated 3-42 months)	Bayley Scales of Infant and Toddler Development 3 rd Edition (Bayley-III)
>2.5-6 years (validated 2.5–7 years)	Wechsler Preschool Primary Scale of Intelligence (WPPSI–IV)
>6 years (validated 6-16 years)	Wechsler Intelligence Scale for Children (WISC-IV, or WISC-V if released prior to trial commencement)

The Vineland Adaptive Behaviour Scales (Vineland-II) assesses personal and social skills needed for everyday living and is validated for use across the lifespan (birth-90 years). This assessment will be used in the parent/caregiver reporting format for all participants, to allow use for children with severe CP who would not be able to complete the assessment on their own behalf. 30 mins to administer (parent)

The Behaviour Rating Inventory of Executive Function (BRIEF) will be used to provide information on how problems such as attention difficulties, poor working memory, disinhibition and planning/organisational impairments impact everyday behaviour. The BRIEF is used for 5-18 year olds, the preschool version BRIEF-P is used for 2-5 year olds. It is a parent questionnaire of 86 items. 15 mins to administer (parent)

The Strengths and Difficulties Questionnaire (SDQ) is a brief series of 25 questions for parents which, although broad, correlate well with more detailed assessment tools. A set of Australian norms are available. This tool can be used for 2-16 year olds (parents of 2-4 year olds receive a slightly modified version). 5 mins to administer (parent)

The Beery-Buktenica Developmental Test of Visual-Motor Integration (Beery VMI) is a virtually motor-free assessment for children. 15mins to administer (participant)

## 8. REPORTING ADVERSE EVENTS

### Definitions

An adverse event (AE) is defined as any untoward medical occurrence in a patient enrolled in this study, whether due to study treatment or not. All AEs will be recorded and evaluated by study doctors, and their relationship to the treatment will be assessed. AEs are limited to those that initiate or worsen during the course of the trial. AEs will be categorised by severity according to Appendix 13: Categorising severity of AEs related to study treatments: NCI Common Terminology Criteria for AEs (CTCAE).

A serious adverse event (SAE) is an AE that is life threatening; may require immediate hospitalisation or transfer to intensive care unit; results in persistent or significant incapacity or even death. It also includes any AE that requires immediate medical intervention to prevent any of these listed consequences. Severity grades 4 and 5 will automatically be designated as a SAE, some discretion by the study doctor may be required for grade 3.

A suspected unexpected serious adverse reaction (SUSAR) is any unexpected SAE that is suspected to be related to the study treatment. For example, infusion-associated graft-versus-host disease (GvHD) and anaphylaxis are potential risks that may be classified as SUSARs.

### Eliciting Adverse Event information

Adverse events will be recorded from the time of infusion until the last visit (12 months post infusion). During the UCBC infusion patients will be monitored at 5 minute intervals, then during hydration every 30 minutes. On leaving the hospital, the patients and their families will be provided with contact details and

asked to contact the study team if any unusual health change should occur. They will also be provided with a card to provide to a treating doctor should the participant require an unscheduled visit, particularly other than at the study site hospital. The card provides details for either the family or the admitting doctor to notify study doctors of potential SAEs to ensure information is elicited, and reported, as early as possible.

The transplant physician will conduct a medical assessment on the day after infusion to assess late reactions to infusion (eg. fever, signs of renal insufficiency), and each week (to detect signs of GvHD) until the 1 month follow up physical examination. At each study visit patients will be asked how they feel and how they have felt in the period since the last visit. They will also be asked if they have had any accidents, illnesses, been hospitalised or changed medication. AEs will also be documented from findings of physical examination.

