#### 4.3. Primary and secondary outcome measures

The primary objective of this study is to collect initial safety data during and after infusion of sibling UCBCs. The following outcomes will be collected to assess this objective which will be assessed at three time points:

- 1) During the infusion and up to 36 hours after
  - Clinical assessment, including vital signs and pulse oximetry
  - Laboratory assessment looking for markers of infection

- Occurrence of AEs and SAEs
- 2) Within the three months after infusion
  - Clinical assessment
  - Laboratory assessment looking for markers of immune reaction
  - Deterioration of motor function as assessed by Gross Motor Function Measure
  - Occurrence of AEs and SAEs
- 3) Within the 12 months after infusion
  - Clinical assessment
  - Deterioration of motor or cognitive function as assessed by the appropriate tool (see section 7.3)
  - Occurrence of AEs and SAEs

The secondary outcomes include:

- Efficacy of the intervention at 3 months measured by therapists on a suite of standardised psychometrically sound measures of movement, cognition and quality of life. This will be assessed in an exploratory fashion only. The areas for assessment were selected to focus on motor outcomes because CP is a primarily motor disorder; on cognitive outcomes that have shown change in an international trial [49] and anecdotally from private stem cell clinics (changes in wakefulness, attentiveness and alertness have been described); and how these might affect the participant's life; The motor and quality of life outcomes will also be measured at 3 months. Cognition will be measured at 12 months after infusion and used to calculate change from baseline. Again, the analysis of the 12 month data will be exploratory in nature.
- Understanding the longevity of infused cells. This will be achieved using chimerism studies (engraftment analysis), looking for infused cells circulating in a sibling recipient's blood. We will study chimerism by extracting circulating cell free DNA from plasma and using a new quantitative PCR method detecting differences in copy number deletions between the recipient and donor. It will be reported as the fraction of donor DNA in the sample at each time point for each individual, and constitutes both a safety and mechanistic study.

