Hydration:      All participants will receive intravenous hydration, starting 2 hours prior to infusion and continuing for 4 hours after the conclusion of the infusion. This is to ensure good clearance of any residual red blood cells and free haemoglobin following infusion. Hydration will continue until urine is clear and there is no indication of hypertension. 0.9% NaCl (normal saline)  
125 mL/m^2/hr for a total of 6 hours  
Ordered by transplant physician or delegate  
Infused by nurse

Pre-Medication Ordered by transplant physician or delegate  
Administered by nurse

Medication	Administration	Timing	Reason
Hydrocortisone 25-100 mg	Intravenous	2 hours prior to infusion	To prevent allergic reaction
Antihistamine*	Oral or intravenous	1 hour prior to infusion	To prevent allergic reaction
Paracetamol	Oral	1 hour prior to infusion	Pain prevention
Ondansetron	Oral	1 hour prior to infusion	Nausea prevention

\* The antihistamine will be selected according to clinical indication. Promethazine (Phenergan), which has sedative properties, may be used for children with saliva and airway control, but if there is concern about the airway cetirizine (Zyrtec) or other antihistamines may be used.

Infusion: Intravenous (foot, hand or antecubital fossa)  
Catheter size as above (compromise between smallest being easiest for children, whilst remaining large enough to prevent cell damage)  
Infused over the course of 10-20 mins depending on age of the participant  
Maximum volume of infusate is 10 mL/kg recipient  
Ordered by transplant physician or delegate  
Infused by nurse  
Additional infusion identity check by study staff

Minimum TNC: > 1 x 10^7 cells/kg body mass (in line with other international trials)

In the case of a Rh+ donor and Rh- recipient, the transfusionist or transplant physician will order anti-Rhesus D immunoglobulin (Anti-D) from the hospital blood bank, which will be delivered by i.v. or i.m. injection 24 hours after infusion (at visit 4) to prevent development of antibodies. The Anti-D administration is precautionary, the red blood cell depletion of CBUs and lysing of remaining red blood cells during cryopreservation combined with the CBU washing procedure means there should be negligible red blood cell antigens (ABO, rhesus, Kell or others) remaining.

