
Cytokine release syndrome Definition: A disorder characterized by nausea, headache, tachycardia, hypotension, rash, and shortness of breath; it is caused by the release of cytokines from the cells.
	
 
•
 
	
Mild reaction; infusion interruption not indicated; intervention not indicated
	
Therapy or infusion interruption indicated but responds promptly to symptomatic treatment (e.g., antihistamines, NSAIDS, narcotics, IV fluids); prophylactic medications indicated for ≤24 hrs
	
Prolonged (e.g., not rapidly responsive to symptomatic medication and/or brief interruption of infusion); recurrence of symptoms following initial improvement; hospitalization indicated for clinical sequelae (e.g., renal impairment, pulmonary infiltrates)
	
Life-threatening consequences; pressor or ventilatory support indicated
	
Death

Infection
						

Catheter related infection Definition: A disorder characterized by an infectious
	
 
• Within 24 hours of infusion
 
	
-
	
Localized; local intervention indicated; oral
	
IV antibiotic, antifungal, or antiviral intervention indicated; radiologic or
	
Life-threatening consequences;
	
Death

process that arises secondary to catheter use.			intervention indicated (e.g., antibiotic, antifungal, antiviral)	operative intervention indicated	urgent intervention indicated	
Respiratory infection Definition: A disorder characterized by an infectious process involving the respiratory tract.	• Throughout study	-	Moderate symptoms; oral intervention indicated (e.g., antibiotic, antifungal, antiviral)	IV antibiotic, antifungal, or antiviral intervention indicated; radiologic, endoscopic, or operative intervention indicated	Life-threatening consequences; urgent intervention indicated	Death
Procedural complications						
Bruising Definition: A finding of injury of the soft tissues or bone characterized by leakage of blood into surrounding tissues.	• During or immediately after needle	Localized or in a dependent area	Generalized	-	-	-

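### Section 8 contradicts itself on when adverse event recording starts, so events between cannulation and the start of the cells fall outside the recording period and all three primary windows

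*Protocol*

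**What the plan says.** Section 8 of the Protocol makes three statements about which AEs are captured.

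- Under Definitions, an AE is "any untoward medical occurrence in a patient enrolled in this study, whether due to study treatment or not". It must begin or worsen while the trial is running, and all AEs are to be recorded.
- Under Assessment and Documentation of Adverse Events, the investigator must record every AE, whether or not it is linked to the study.
- Under Eliciting Adverse Event information, "Adverse events will be recorded from the time of infusion until the last visit". This is the only sentence in the Protocol that fixes a start.

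Section 4.3 sets three primary safety windows: "During the infusion and up to 36 hours after", "Within the three months after infusion" and "Within the 12 months after infusion". Section 9 summarises safety as the proportion of participants with an AE and with an SAE in each window, and gives no earlier start.

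Section 5.5 describes the infusion day: "All participants will receive intravenous hydration, starting 2 hours prior to infusion". Intravenous hydrocortisone is also timed two hours before, and antihistamine, paracetamol and ondansetron one hour before. A peripheral cannula is placed first.

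**The concern.** Safety is the primary objective, and the AE and SAE proportions are its main summary. Section 10 says that the procedures in the Protocol are for research rather than routine care, so the cannula, fluids and premedication are exposures that the trial imposes. A site that follows the stated start would leave out a reaction to any of them that begins before the cells. A site that follows the definition would record it. The two infusion hospitals could therefore count the same event differently. The error from omission runs one way: it lowers the reported proportions. The Data Safety Monitoring Committee reviews after the first three and first six children draw on the same safety data.

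**Working it through.** No sample size, power or alpha figure bears on this point. The check sets the infusion-day clock of Section 5.5 against the recording rule and the windows, with time 0 as the start of the cells.

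**Inputs (Section 5.5)**
- Hydration: from -2 h until 4 h after the infusion ends. The Protocol's own total is reproduced: 2 h + 4 h = 6 h, not counting the 10-20 minutes of the infusion itself.
- Hydrocortisone (intravenous): -2 h.
- Antihistamine, paracetamol, ondansetron: -1 h.
- Cannula: no clock time is given. Fluids and an intravenous drug start at -2 h and this is the only line described, so it must be in place at or before -2 h.

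**Rules**
- Recording (Section 8): from 0 to the last visit at 12 months.
- First window (Section 4.3): 0 to +36 h after infusion.
- Second and third windows: after infusion, to 3 and 12 months.

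**Where an event falls, by onset**
1. Onset between cannulation and 0, not worsening later: before the recording start and in none of the three windows. It is still an AE by the Definitions paragraph, because the child is enrolled and the trial is running.
2. Onset before 0, worsening after 0: recorded, because the definition includes events that worsen.
3. Onset at or after 0, including delayed drug reactions, later cannula-site problems and the remaining 4 of the 6 hydration hours: recorded and in a window.
4. A reaction before 0 that leads to the infusion being cancelled: there is no time of infusion, so recording never starts and no window opens for that child.

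Only cases 1 and 4 are lost from the AE and SAE proportions.

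**Size per child**
- Full study: 1/12 = 0.083, or 8.3 percentage points.
- First six children: 1/6 = 16.7 points. First three: 1/3 = 33.3 points.

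A proportion moves by this amount only if the child has no other counted event of that type in that window and the denominator is the number shown. The 36-hour window is more exposed than the 12-month one, because a longer window leaves more room for another event.

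**The case against.** The strongest reply is that the time of infusion can mean the whole of visit 3. Section 5.5 is titled for the infusion visit, the Section 6 schedule labels that phase as infusion at time 0, and cannulation, fluids and premedication are all described there. This reading is possible. But Section 5.5 times the fluids and drugs relative to the infusion, and so uses the word for the cells alone. The wider reading would also leave the first window in Section 4.3 opening during the infusion. If both readings are open, sites may differ.

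A second reply is that other text closes much of the gap. Section 7.1 has vital signs taken before the infusion. Section 8 asks at each visit how the child has been since the last one, and documents AEs from physical examination. SAE reporting to the ethics committee carries no infusion-based start. These help an event to be noticed. None of them sets a recording start or places the event in a window.

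Several stronger readings are tempting, and the documents do not support them.

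- A reader might infer that all reactions to the cannula, fluids and premedication are lost. Only those beginning before the cells, and not worsening later, are.
- A reader might take the Appendix 13 rows for bruising and venous injury, timed "During or immediately after needle", as proof of the exclusion. Those rows also fit the blood draws at 24 hours, 1 week, 1 month and 3 months and the possible anti-D injection, all inside the recording period.
- A reader might use the share of infusion-day time before the cells as the share of harm missed. That is clock time, and the Protocol gives no event rate for it.
- A reader might infer that a cancelled infusion leaves no trace. Sections 4.5 and 9 document and report withdrawals with reasons. What is missing is its place in the AE and SAE summary.

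Anchoring the windows to the cells is itself defensible in a descriptive, single-group study whose objective is the safety of the cell infusion. That argues for keeping pre-infusion events on their own line, not for leaving them unrecorded.

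**Conclusion.** The contradiction is real and modest. The Definitions and Assessment paragraphs of Section 8 cover enrolled children over the course of the trial. The Eliciting paragraph and the first window in Section 4.3 begin at the infusion. Under the stated start, events with onset in at least the two hours before the cells are omitted for all 12 children unless they worsen later. The direction is toward too few events. The size is 8.3 points per affected child in a proportion out of 12. The total cannot be estimated, because the Protocol gives no frequency for pre-infusion reactions, and many may be minor.

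This rests on two assumptions: that the time of infusion means the start of the cells, as Section 5.5 uses the word, and that the cannula is the line through which the -2 h fluids and drug are given. If the first is relaxed to the whole of visit 3, the recording gap closes but the first-window gap in Section 4.3 remains.

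**What to change.** Reconcile the Definitions and Eliciting paragraphs of Section 8 with Section 4.3:

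- Start AE recording at the first trial procedure on the infusion day, whichever of cannulation, hydration or premedication comes first.
- State that a child whose infusion is cancelled after that point is included.
- Keep the three windows anchored to the cells, and report events with onset before the cells on a separate line for pre-infusion procedures beside them.
- Align the AE definition with that start, so that one rule applies at both infusion sites.

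The cost is a short wording change in Sections 8 and 4.3, a field on the case report form to mark onset before or after the start of the cells, and a few more minor events in the report. Sample size and treatment are unaffected. Going back to the first study blood sample at visit 1 is not proposed. It would extend recording to up to 48 screened children, about 75% of whom the Protocol expects to exclude as unmatched, and would add events that say little about infusion safety.

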#### *Assessment and Documentation of Adverse Events*

AEs will be reported to the investigator by the infusion team, family or assessing paediatrician or therapist. The investigator is then responsible for recording all AEs, regardless of their association with the study.

The documentation of each AE will include a description of the AE and its severity, timeline, action or treatment required and the outcome. After discussion with the study team, the likelihood that the AE was the result of the study intervention will be assessed as unrelated, possible, probable or definite.

All AEs will be followed until resolved, and changes in the AE or repeated episodes will be documented for retention and publication.

#### *Serious Adverse Event Reporting*

Should an AE be categorised as serious, the local HREC will be notified within 72 hours of its occurrence using Appendix 12: Serious adverse event report form. The HREC safety reporting form will be completed, signed and submitted by the coordinating principal investigator with the trial coordinator. Should there be a SUSAR, HREC will be notified within 72 hours as with a SAE. All SUSARs occurring in a study participant will be reported to the Therapeutic Goods Administration (TGA) within 2 weeks of first occurrence. The report will be completed, signed and submitted by the coordinating principal investigator with the trial coordinator.

Graft-versus-Host Disease (GvHD) of Grade II or above (as defined in Appendix 13:) will stop the trial. The DSMC may advise stopping the trial if other SAEs occur, based on clinical discussion of the SAE and its potential relationship to the study treatment.

